8.2. Blinding

This is a retrospective, observational study. This trial is not blinded.

9.0. Methods: Data Collection, Management, and Analysis

9.1. Data Collection Methods

The women with CF who are enrolled at any of the 10 CF centers will complete the contraceptive and reproductive health questionnaire. We will ask for exposure data as far back as 2008. One way we will improve exposure data will be to reduce recall bias with pictures of most birth control pill packages and other birth control methods. Exposure questions will be piloted as described in 6.0 above. Survey responses will be entered directly into a REDCap database which will be developed at UW. REDCap is HIPAA compliant and securely accessible from anywhere with Internet access, and feasibly merges data from separate REDCap databases into a single database. Next, UW will send the CFFPR a list of patient names, their birthdates, and CFFPR ID. The CFF will provide UW with their CFFPR ID and requested registry data. UW will assign a central ID number for each participant, so that data from each of the databases can be connected for analysis. We will import data from CFFPR using Excel into a REDCap database housed at UW.

Data will be collated at the UW. When a computer is available, participants will answer directly into the database, which leaves less room for transposing errors. In case of technical difficulty with computer access to the REDCap website, the clinical site will receive paper source documents. Each survey (online and paper) will be identified by the participant's study number.

9.1.1. CFFPR Data Elements

A complete list of data points being requested from CFFPR are in the Appendix.

9.1.2. Clinic Case Report Forms (CRF)

We are requesting CRFs from each of the 10 CF centers in order to verify DXA scan findings with bone data reported in the CFFPR.

Table 9: Information sought on CRF

EMR Data Request

• DXA scan results: dates and results as far back as 2013. Results will include T-scores and Z-scores from 3 sites: femoral neck, lumbar spine, and total hip and date that DXA scan was performed.

9.1.3. Patient Surveys

Table 10: Information in online, self-respondent surveys

Survey O	nce Enrolled
• Demog	graphics: marital status, race/ethnicity, and education
	nedical history: ever smoked, ever had a blood clot requiring anticoagulation, # PICC lines placed, PORT in (dates)
Medic	ation history: ever taken CFTR modulator (with start and stop dates)
-	al history: Tubal ligation, hysteroscopic sterilization, hysterectomy, bilateral oophorectomy, other operation as made it impossible to get pregnant
• Menst	rual history: menarche, regularity of menstruation, menopause
• Contra	aception questionnaire
•	Questions regarding types of contraception used since 2008, start and stop dates of each method or age at first/last use. Questions are based off of the National Survey of Family Growth (NSFG)
• Pregna	ancy history questionnaire

- - Includes number of pregnancies in lifetime, year(s) pregnant, outcome of pregnancy, whether pregnancy was planned or not
 - Additional questions to include for funded study ([name] and [name]): times visited CF center during pregnancy and type of provider who cared for participant during pregnancy, ART

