4.2. Secondary Study Objectives/Endpoints

- To assess the association of hormonal contraceptive use on trends in lung function (FEV1) over time, compared to non-hormonal contraceptive users (primary control) and non-contraceptive users (secondary control).
- To assess the association of hormonal contraceptive use on the incidence of venous or arterial thromboembolism.
- To assess the association of hormonal contraceptive use on prevalence of liver dysfunction, defined as gallstones (requiring surgery), hepatic steatosis, hepatic cirrhosis, and/or incidence of increased liver enzyme test values (ALT/GGT). Increased liver enzymes is defined as exceeding upper limit of normal on at least 3 occasions over 12-month period.
- To assess the association of hormonal contraceptive use on serum glucose trends, incidence of insulin resistance or time to CF-related diabetes (requiring insulin treatment).

- To assess association of hormonal contraceptive use on nutritional status through the evaluation of BMI trends.
- To validate bone health information in CFFPR with chart data obtained from one CF center (limited due to need for data use agreements between institutions for EMR data).
- To determine if those using hormonal contraception while using CFTR modulators report higher rates of unintended pregnancy compared to those taking non-hormonal contraception.
- To assess proportion of mucoid *P. aeruginosa*, in patients who are *P. aeruginosa* positive, among hormonal contraception users compared to non-hormonal contraceptive users.

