7.5. Outcomes (include DAG diagrams to show relationships between exposure and outcomes)

Table 5: Outcomes and associated confounders and covariates

Exposure of interest	Outcome	Confounders/Covariates	Rationale
Combined	Pulmonary outcomes	Smoking	Affects lung function
hormonal contraception (CHC)	 Annual pulmonary exacerbation rate (PEx) (defined as episodes requiring intravenous 	Insurance status (reflection of SES)	Will be used as socioeconomic indicator. Less access to meds may mean less
&	antibiotic use at home or in		compliance
Progestin-only	hospital)Absolute change in FEV1 (in	Age	Lung function worsens as one ages
contraception	liters) Prevalence of micro-organism (defined as 1 or greater sputum	Education (reflection of SES)	Affects contraceptive knowledge decision making
	culture within a 12-month period)P. aeruginosa	ВМІ	Associated with better or worse health status in general

Exposure of interest	Outcome	Confounders/Covariates	Rationale
	 MDR P. aeruginosa Staph aureus 	Exercise	May reduce pulmonary exacerbation rates
	MSSA MRSA	CF genotype class	Associated with severity of disease
	Secondary infections: • Burkholderia cepacia	CFTR modulator treatment	Likely preserves pulmonary decline
	 Burkholderia cenocepacia Mycobacterial species –includes M. tuberculosis and NTM species 	Comorbidity with CFRD (defined as requiring chronic insulin therapy) (11)	Associated with worse disease (reduced immunity)
		Length of hormonal contraceptive use (person-year of exposure)	
	Venous/arterial thromboembolism (VTE)	BMI ≥ 30	
	 Noted on self-respondent survey (defined as blood clot requiring anticoagulation treatment) 	Age > 35 years PMHx for thrombophilia Arterial/venous lines or ports Pmhx cancer Smoking	
	Liver outcomes	BMI	Obesity contributes to
	 Liver disease, non-cirrhosis Gallstone, requiring surgery/procedure (defined as present or absent as 	Comorbidity with diabetes	liver dysfunction Associated with worse disease (reduced immunity)
	recorded in CFFPR)	Hepatitis	Risk factor for liver dysfunction
		CF genotype class Length of hormonal contraceptive use (person-year of exposure)	
	 Serum ALT, GGT (meets criteria if hepatic transaminases and GGT levels exceed upper limit of normal on at least 3 consecutive occasions over 12-month period) (12) 		Will track meeting criteria annually over time
	CF-related diabetes		
	 Serum ogtt trends New onset insulin resistance or diabetes (defined as 		

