9.3. Statistical Methods

Because this is a retrospective cohort study, we are most interested in determining whether this exposure (to hormonal contraception) is associated with our primary outcome (counting the number of pulmonary exacerbations requiring additional IV in a given year) and/or our secondary outcomes (new respiratory microbiology, liver disease/non-cirrhosis, gallstone, requiring surgery/procedure, improved BMI, incidence of VTE, osteoporosis and fragile bone fracture). Women on hormonal contraception will be compared to the primary control group of women on non-hormonal contraception. We will also compare to women on no contraception, as the secondary control group. We will exclude persons with these existing diagnosis at the start of the follow up period for outcome data (January 1, 2010). Within this objective we will be able to calculate incidence rates, relative risks and confidence intervals. We will use Poisson regression to calculate progestin-only and combined hormonal method to non-hormonal method pulmonary exacerbation rate ratios and 95% confidence intervals. This allows for adjustment of follow-up time of each individual.

(Objective 1a): We will evaluate lab values over time (ppFEV1%, serum AST, ALT, alkaline phosphatase) to determine if trends between hormonal contraceptive users and non-hormonal contraceptive users differ. See Table 5 for confounders and covariates that we will use to adjust for the primary and secondary outcomes.

We will model ppFEV1 via generalized estimating equations (GEE), allowing for correlation within a subject, and compare via a fixed effect for exposure. Among women who change or stop contraception, we will estimate and compare within-participant difference in outcomes via the model (if numbers allow). We will censor women who switch method types or become pregnant, and for 6 months post pregnancy, for the primary analysis and subsequently follow them to leverage within-patient data and analyze changes in pulmonary status and contraception. Presence of respiratory microbiology will be estimated longitudinally via GEE with a logit link function. Graphic displays and summary statistics will be used; all *p* values will be two-sided.

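### Thromboembolism is planned as an incidence endpoint, but its only specified source is a lifetime survey item with no event date or event type

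*Combined protocol and SAP*

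**What the plan says.** Section 4.2 lists this secondary objective: "To assess the association of hormonal contraceptive use on the incidence of venous or arterial thromboembolism". Table 5 in Section 7.5 gives the source and case definition: "Noted on self-respondent survey (defined as blood clot requiring anticoagulation treatment". Section 9.3 includes the incidence of VTE among the secondary outcomes, and Table 5 uses that abbreviation for venous and arterial events together. Section 9.3 also promises incidence rates and relative risks, and sets the start of observation: "We will exclude persons with these existing diagnosis at the start of the follow up period for outcome data (January 1, 2010". Women who switch method type or become pregnant are censored in the primary analysis. In Table 10 (Section 9.1.3) the medical-history entry reads "ever had a blood clot requiring anticoagulation, # PICC lines placed", followed by the port item, after which the word dates in brackets closes the entry.

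**The concern.** Incidence on a given contraceptive method needs two things for each event: when it happened, and which method the woman was using then. Contraceptive exposure is collected with timing from 2008 onward, but the documents specify no timing for the clot. Three women would then give the same answer: one with a clot in her teens before any method, one with a clot while on an estrogen-containing method, and one who changed to a non-hormonal method after a clot. Research question 2 and the second hypothesis both name thromboembolism as a possible harm of hormonal methods. The comparison at stake is therefore one of the study's stated safety questions.

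**Working it through.** The plan gives no event rate, sample size or power for thromboembolism, so there is no figure to reproduce. The check compares the data sources with what the analysis needs, and then gives one illustration.

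**Step 1: what each source supplies.**
- *Survey, Table 10.* The clot item asks about lifetime occurrence. The word dates at the end of the entry most naturally belongs to the port. The same table specifies timing for modulators ("ever taken CFTR modulator (with start and stop dates"), for contraception ("start and stop dates of each method or age at first/last use") and for pregnancies (by year).
- *Participant tasks, Table 7.* Smoking and clot questions are listed together, with no mention of a date.
- *Clinic case report form, Table 9 (Section 9.1.2).* DXA results only.
- *Registry Appendix, described as complete in Section 9.1.1.* It requests diabetes, renal, liver, bone and cancer complications, but no clot, stroke or anticoagulant variable. Section 1.0 says linked registry data will be used for thromboembolism, yet no variable on the list would do this.

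**Step 2: what Section 9.3 needs.**
- Removing cases that existed at January 1, 2010 needs the event date.
- A rate by method needs the event date set against the contraceptive history.
- Censoring at switch or pregnancy needs the order of event and censoring.

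Without a date none of these can be done for a clot. What remains is a yes or no for lifetime history. A clot before 2008 has no matching exposure data, and without a date it cannot be recognised as such.

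**Step 3: illustration of how many lifetime reports could predate 2010.** Assumptions, none of them from the documents except the age counts: constant hazard from age 15; the Table 3 numbers (383 aged 18-35, 192 aged 36-45) spread evenly over 18 to 36 and 36 to 46; survey in mid-2020 or mid-2021, that is 10.5 or 11.5 years after January 1, 2010. The share is person-time before 2010 divided by all person-time since age 15.
- Total: 383 × (27 − 15) + 192 × (41 − 15) = 4,596 + 4,992 = 9,588 years.
- Mid-2020, time before 2010 = max(0, age − 25.5): 383 × 10.5²/(2 × 18) + 192 × 15.5 = 1,173 + 2,976 = 4,149. Share 4,149/9,588 = 43%.
- Mid-2021, time before 2010 = max(0, age − 26.5): 383 × 9.5²/(2 × 18) + 192 × 14.5 = 960 + 2,784 = 3,744. Share 3,744/9,588 = 39%.
- By age band: 36-45 gives 15.5/26 = 60% and 14.5/26 = 56%. 18-35 gives 3.06/12 = 26% and 2.51/12 = 21%.
- Starting risk at age 18 or 12 instead of 15 moves the overall share to 34-49%.
- If the hazard rises linearly from age 15, years are replaced by squared years. Total: 383 × 171 + 192 × 684.3 = 196,885. Before 2010: 55,939 (mid-2020) or 48,049 (mid-2021). Share 28% or 24%.

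**Step 4: the mix depends on age.** Take a 2021 survey, the same constant hazard and outcome years 2010-2018. A woman aged 25 has 10 years at risk, 8 of them in the window (80%). A woman aged 45 has 30, of which 9 are in the window (30%). Lifetime reports therefore mix events before, during and after follow-up, in proportions that change with age.

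**The case against.** The strongest reply is that Table 10 is a topic list and not the questionnaire, which is not in the documents. Sections 6.0 and 7.0 say the questions are pre-tested and revised before the full study. The line with the bracketed word is damaged in the text, and the word could cover the whole entry. The table is also uneven: it gives no dates for sterilisation, hysterectomy or menopause either. This stands to the extent that nobody can say from these documents that the instrument lacks a date. They show only that none is specified.

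Four stronger readings are tempting, and the documents do not carry them.
- *The comparison would be biased towards showing no harm.* A clot that led to a switch could be counted among controls. A clot before any method, in a woman who later used a hormonal one, could be counted against hormonal use. The plan does not say how a lifetime clot would be assigned, so the net direction is unknown.
- *Arterial events are being missed because the definition requires anticoagulation.* The documents do not say how any arterial event is treated, so this needs outside knowledge. What they do show is that the objective names both types and the item records neither.
- *Line-related clots must be separated.* Table 5 lists lines and ports only as covariates. A count of PICC lines with port dates partly serves that purpose, and the plan promises no separation.
- *About two in five reports will be too early.* That figure depends on the assumed hazard, and no clot rate is given from which to derive event numbers or a bias in the rate ratio.

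**Conclusion.** The point holds as a mismatch between endpoint and data source. The plan specifies "incidence of venous or arterial thromboembolism" as the endpoint, but as written it collects only lifetime history of a clot, with no event date or type and no second source. The exclusion at January 1, 2010, the attribution to method and the censoring rule cannot be applied to it. The illustrative share of reports predating 2010 is about 39-43% under a constant hazard from age 15 and about 24-28% under a linearly rising one. Both rest on assumed survey dates and an assumed risk pattern, and indicate scale only. This is a secondary safety endpoint with no power claim, and the primary exacerbation analysis is unaffected. It should be corrected before fielding, because the design plans one survey per woman.

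**What to change.** - *Table 10:* for women who answer yes, add the month and year (or age) of each clot and whether it was venous or arterial. If the questionnaire already asks this, say so in the table.
- *Table 5:* define the outcome as the first dated event after January 1, 2010 and within the follow-up window, attributed to the method in use according to the dated contraceptive history. Align the case definition with the venous and arterial wording of Section 4.2, and use the same term in Section 9.3.
- *If dates are not collected:* relabel the endpoint in Sections 4.2 and 9.3 as lifetime history of a clot and drop the incidence claim.
- *Optional:* year of placement for each PICC line.

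The cost is a few branching questions shown only to women who report a clot, with no extra participants. The downside is some recall error in the dates.

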2.0. Background/Rationale

Family planning decisions are increasingly important for women with CF as most reach reproductive age in reasonable health. As CF care management and directed therapies advance, the number of women with CF in the US over age 18 has nearly doubled over the last 15 years: from 4,000 to 7,200. The CFF has an existing comprehensive patient registry, the CFFPR, which captures annual data on over 90% of all persons with CF in the US (1). While it is comprehensive regarding most aspects of CF patients' health, the CFFPR currently only asks one question that addresses reproductive health for women over 18 living with CF: "Was the patient pregnant during the reporting year?".

Reliable information is urgently needed to enable healthcare providers to help CF women understand the effectiveness and safety of current contraceptive methods for them. While infertility usually affects men with CF, at least 50% of women with CF are estimated to be physiologically capable of becoming pregnant without fertility treatment (2); however, that percentage is expected to rise with the use of new life sustaining medications, such as the CFTR modulators and especially the newly Food and Drug Administration (FDA)-approved triple-combination modulator, TRIKAFTA® (3).

Our recently completed survey study among 150 women at three CF centers, suggests that only about 60% of reproductive—aged women with CF are using contraception (4). Among those who are, oral contraceptive pills (OCPs) and condoms are the most commonly reported methods. Gaps in quality contraceptive care for women with CF exist, in part because, surprisingly, women with CF prefer to receive their sexual health care within the CF clinics, but many CF providers do not feel prepared to deliver safe and detailed contraception care (5). This information gap is exacerbated by the limited data which exist to inform contraceptive care provision for women with CF. In fact, most studies evaluating contraceptive safety are limited to oral contraceptive pills, even though the number of choices of FDA-

CASE.4.CF Study Protocol

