 - Race includes 'Some other race'
 - Patient is Hispanic
- Health insurance
 - Health insurance policy (i.e. private insurance)
 - Medicare
 - o Medicaid
 - State special needs program (BCMH, CCS, CRS, GHPP...)
 - TriCare or other military health plan
 - o Indian Health Service
 - Other health insurance
 - o Patient has no health insurance for the entire year
 - Patient covered on their parents' insurance plan
 - o Receives free medicine/assistance from patient assistance program
- Socioeconomic characteristics
 - Patient's education
- Smoking
 - Patient smokes cigarettes during the reporting year
- Research involvement
 - o Patient participated in interventional (drug) studies
- Patient pregnancy
 - o Patient was pregnant during the reporting year
 - Outcome of patient's pregnancy

II. DIAGNOSIS

- Diagnosis date
 - First year in the CFF Patient Registry
 - Research involvement
 - Patient participated in interventional (drug) studies
- Genotyping
 - \circ $\;$ Has this patient been genotyped
 - Mutation classification
 - Name of the first mutation
 - Mutation 1 Class
 - Name of the second mutation
 - o Mutation 2 Class
 - o Delta F508

III. CLINIC VISITS

• Visit details

- Date of Encounter [PHI]
- Encounter age [PHI]
- Pulmonary exacerbation encounter level
 - Assessment of potential pulmonary exacerbation
- Pulmonary exacerbation summarized by calendar year
 - o Any pulmonary exacerbation assessment in the year
 - Any pulmonary exacerbation assessment positive in the year
 - # encounters with pulmonary exacerbation assessments: absent
 - o # encounters with pulmonary exacerbation assessments: mild exacerbations
 - o # encounters with pulmonary exacerbation assessments: moderate exacerbations
 - # encounters with pulmonary exacerbation assessments: severe exacerbations
 - Encounter exacerbation treatment: Incr. airway clearance
 - Encounter exacerbation treatment: Oral NON-quinolone antibiotic
 - Encounter exacerbation treatment: Oral quinolone antibiotic
 - Encounter exacerbation treatment: Inhaled Antibiotic
 - o Encounter exacerbation treatment: Inhaled + Oral NON-quinolone antibiotic
 - Encounter exacerbation treatment: Inhaled + oral quinolone antibiotic
 - Encounter exacerbation treatment: None of the above

IV. CLINICAL MEASUREMENTS

- Anthropometric measures encounter level
 - Patient's height
 - BMI Value
 - BMI Percentile
 - Weight of Patient
- Pulmonary function tests encounter level
 - Measure of FVC

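### As listed, pregnancy is dated only by calendar year, too coarse for the 6-month post-pregnancy censoring and for attributing unintended pregnancies to the method and modulator in use at conception

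*Combined protocol and SAP*

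**What the plan says.** **What is collected.** The pregnancy line of Table 10 (section 9.1.3) reads: "Includes number of pregnancies in lifetime, year(s) pregnant, outcome of pregnancy, whether pregnancy was planned or not". From the registry, the Appendix (I. Demographics) requests "Patient was pregnant during the reporting year" and the outcome of the pregnancy. Section 2.0 describes the registry's single reproductive-health question in the same yearly terms ("Was the patient pregnant during the reporting year"), and section 9.1.1 states: "A complete list of data points being requested from CFFPR are in the Appendix". The clinic forms serve another purpose (section 9.1.2): "We are requesting CRFs from each of the 10 CF centers in order to verify DXA scan findings with bone data reported in the CFFPR".

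**What the analysis needs.** Section 9.3 states: "We will censor women who switch method types or become pregnant, and for 6 months post pregnancy, for the primary analysis". Section 4.2 sets a secondary objective: "To determine if those using hormonal contraception while using CFTR modulators report higher rates of unintended pregnancy compared to those taking non-hormonal contraception". Research question 6 in section 2.0 asks about unintended pregnancy occurring during method use, and section 3.0 adds a hypothesis that oral methods work less well than other hormonal methods when a modulator is taken.

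**Exposure timing.** Table 10 collects start and stop dates for modulators. For each contraceptive it collects either start and stop dates or age at first and last use.

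**The concern.** A rule stated in months is to be applied to an event recorded in years. The other main inputs are finer: the Appendix requests start and end dates of care episodes, and most exposure is to be dated. Pregnancy timing is therefore the limiting input.

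Two uses are affected. In the censored analysis, either post-pregnancy time that the plan means to remove stays in, or valid person-time is lost. For the unintended-pregnancy endpoint, the event of interest is conception while a given method and a modulator are in use. A woman who conceives on the pill can be expected to stop it once she knows she is pregnant. Her record then shows a stop date and an unplanned pregnancy in the same year, as does the record of a woman who stopped first and conceived later. Without a conception month or a method-at-conception item, the two can look the same.

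Section 9.3 gives no year-level censoring rule, no rule for imputing pregnancy dates, no attribution rule and no described analysis of the pregnancy endpoint. The general statement on imputing missing data does not say how to treat dates that were never requested. The choice would be left to the analyst after the data are in hand.

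**Working it through.** The plan gives no figure on this point, so there is none to reproduce.

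**Step 1. Finest pregnancy timing in each listed source**

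| Source | Timing listed |
|---|---|
| Survey (Table 10) | calendar year(s) |
| Registry (Appendix) | reporting year, yes/no |
| Clinic form (9.1.2, Table 9) | none; DXA only |

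**Step 2. Placing the 6-month window from calendar years.** Assumptions, none of them from the documents: conception is uniform over the year, pregnancy lasts 9 months, and every calendar year touched is reported. Let c be the month of conception (0 to 12). Pregnancy ends at c + 9 and the window closes at c + 15. The pregnancy crosses into a second year if c > 3, which is 9/12 = 75% of cases.

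*Rule A: censor only the reported year(s).* Reported time ends at month 12 if c ≤ 3, otherwise at month 24. Window left uncensored:
- c from 0 to 3 (25%): (c + 15) − 12 = c + 3, mean 4.5 months.
- c from 3 to 9 (50%): none.
- c from 9 to 12 (25%): (c + 15) − 24 = c − 9, mean 1.5 months.

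Share affected: 25% + 25% = 50%. Overall mean: 0.25 × 4.5 + 0.25 × 1.5 = 1.5 months. Mean among those affected: 1.5 / 0.5 = 3 months.

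Time removed averages 0.25 × 12 + 0.75 × 24 = 21 months. Of this, 15 − 1.5 = 13.5 months is time the rule means to remove, so 21 − 13.5 = 7.5 months is lost needlessly.

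*Rule B: censor the following year as well.* Every window is covered, but 21 + 12 = 33 months are removed against 15 intended: 18 extra months per pregnancy.

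*Midpoint imputation of the end date.* A two-year pregnancy ends somewhere in a 9-month interval (mean error 2.25 months, maximum 4.5). A one-year pregnancy ends in a 3-month interval (mean error 0.75). Overall mean error is 0.75 × 2.25 + 0.25 × 0.75 ≈ 1.9 months, and 0.75 × (3/9) = 25% are wrong by more than 3 months, half the window.

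*Sensitivity to duration.* A simulation with a 2.5-month loss in place of a term pregnancy gave the same Rule A and B results: 50% affected, 1.5 months left in overall, 7.5 and 18 months over-censored.

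**Step 3. Attribution.** If stopping is uniform over the year, a conception g months after stopping falls in the same calendar year as method use with probability 1 − g/12: 92% at g = 1, 75% at g = 3, 50% at g = 6. These figures are conditional on a conception after stopping. They show how often the year alone fails to separate the two events; they do not say how many pregnancies would be misclassified.

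**The case against.** - **The questionnaire is not in the documents.** Table 10 is a summary and its pregnancy line is worded as inclusive, so a month item may exist. This stands: the point is about the data as listed.
- **Exposure is dated.** A woman with one method and one modulator status throughout the pregnancy year(s) can be attributed without a conception month. This also stands. It confines the problem to women who start, stop or switch in that year, or who give only ages. A reader might infer that neither analysis can be done at all; the documents do not support that.
- **Direction of bias.** A reader might infer that apparent failure is inflated in the hormonal group. The documents do not show this. Women who stop a non-hormonal method and then conceive are misplaced by the same mechanism, and nothing is given on differential stopping. The plan also does not say that any use in a year makes a pregnancy in that year an on-method event.
- **Scope of the censoring rule.** The sentence sits in the paragraph on the lung-function model, so its use for exacerbation counts is likely but not explicit. It also censors switching, which may already remove some of the time at issue.
- **A yearly rule could serve.** Exacerbations are counted per year, so a whole-year exclusion is workable at a cost in person-time. That is true, but the plan states no such rule.

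**Conclusion.** The point holds as a mismatch between the timing that the listed sources provide and the timing that two stated rules need. It is worth correcting, but it does not make either analysis impossible.

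Under uniform timing and 9-month pregnancies, the trade-off lies between leaving part of the window in for about half of pregnancies (1.5 months on average over all) and discarding about 18 extra months for each. Both rules are illustrations; the plan specifies neither. The effect on the exacerbation rate ratio cannot be sized, because the documents give no pregnancy counts. For the unintended-pregnancy endpoint, events may be misclassified in both groups, with the net direction unknown.

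**What to change.** During the pre-test, add three items for each pregnancy since 2008: the month and year it ended, its approximate length, and the contraceptive method, if any, in use in the month of conception. Modulator status in that month follows from the start and stop dates already collected.

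In section 9.3, state that a pregnancy counts as on-method only if the method and the modulator were both in use in the month of conception. Apply the six-month censoring from the derived dates, and say which outcomes it covers. Where the month cannot be recalled, apply a prespecified whole-year exclusion, with a sensitivity analysis.

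With months recorded, the window can be placed to within about one month. The cost is a slightly longer survey and some recall error in months. Sections 6.0 and 7.0 already provide for pre-testing and revision, so the change fits there; after enrollment, participants would have to be contacted again.
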